9.3.2. Interim Analysis

No interim analysis is planned for the study.

9.4. Key Elements of Analysis Plan

Treatment Comparisons

The primary treatment comparison of UMEC/VI with UMEC will be performed on the ITT population.

The other treatment comparisons of UMEC/VI and UMEC with Salmeterol will be performed on the ITT population and ITT ICS free population.

9.4.1. Primary Analyses

The treatment comparison of primary interest will be UMEC/VI versus UMEC for the primary endpoint of change from baseline in trough FEV₁ at Week 24. The primary analyses will be performed using a mixed model repeated measures (MMRM) analysis and will be based on a two-sided hypothesis testing approach on the ITT Population.

In order to account for multiplicity across treatment comparisons and endpoints, a step-down closed testing procedure will be applied whereby inference for secondary and other endpoints or treatment comparisons are dependent upon statistical significance having been achieved for the primary comparison. If the primary comparison is significant i.e. the associated p-value for UMEC/VI versus UMEC for change from baseline in trough FEV₁ at Week 24 is below 0.05, this will allow inference of treatment comparisons (UMECA/VI versus UMEC on all other endpoints, and UMEC/VI versus Salmeterol and UMEC versus Salmeterol on all endpoints including the primary endpoint), which will be declared statistically significant if the associated p-value is below 0.05.

There will be 2 analyses one for one for the German Federal Joint Committee (G-BA) and one for the rest of the world (ROW).

The step-down closed testing procedure only applies to the ROW. For the G-BA statistical inference for secondary and other endpoints or treatment comparisons will not be conditional on achieving statistical significance of the primary comparison.

The primary endpoint of mean change from baseline in trough FEV₁ at the end of Week 24 and secondary endpoint change from baseline in TDI score at Week 24 will both be analysed using MMRM analysis. The MMRM analysis for change from baseline in trough FEV₁ and TDI will include measurements at Treatment Weeks 4, 12 and 24. Treatment group (a categorical variable) will be fitted as the explanatory variable with appropriate pre-defined variables, stratum (number of bronchodilators per day during run-in) and baseline values, fitted as covariates. Visit (nominal) will be fitted as a categorical variable and visit-by-baseline and visit-by-treatment interaction terms will be included to allow treatment effects to be estimated at each visit separately. The variance covariance matrix will be assumed to be unstructured (based on previous experience no issues are expected with fitting models with this matrix structure).

While missing data are not explicitly imputed in the primary MMRM analyses, there is an underlying assumption that the data are missing at random.

The estimated treatment differences between UMEC/VI versus UMEC for each endpoint will be presented with the 95% confidence intervals for the difference and the p-value.

Full details of the analyses to be performed on all primary endpoints will be given in the RAP.

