3. OBJECTIVE(S) AND ENDPOINT(S)

Objectives	Endpoints
Primary	

 To compare the effect of UMEC/VI (62.5/25 mcg once daily) with UMEC (62.5 mcg once daily) on lung function 	
 Change from baseline in trough Forced Expiratory Volume in One Second (FEV₁) at week 24
Secondary	

 To compare UMEC/VI (62.5/25 mcg once daily), UMEC (62.5 mcg once daily) with salmeterol (50 mcg twice daily) on patient reported outcomes (PROs) 	
 Change from baseline in self administered computerised (SAC) transient dyspnea index (TDI) Percentage of TDI responders according to SAC TDI score. A responder is defined as a ≥ 1 unit improvement in SAC TDI score Assessment of respiratory daily symptoms over 24 weeks using Evaluating Respiratory Symptoms-COPD (E-RS) and its subscales (breathlessness, cough and sputum and chest symptoms) Percentage of E-RS responders according to E-RS score (defined as reduction in E-RS score of ≥ 2 or ≥ 3.35 units) from baseline

Objectives	Endpoints
	
 Change from baseline in St George's Respiratory Questionnaire (SGRQ-C) Percentage of responders according to SGRQ-C total score (defined as a 4 point or greater reduction from baseline) Change from baseline in COPD assessment test (CAT) Percentage of responders according to CAT (defined as a ≥ 2 unit improvement in score from baseline)
Other 
 To compare UMEC/VI (62.5/25 mcg once daily), UMEC (62.5 mcg once daily) with salmeterol (50 mcg twice daily) on other COPD efficacy measures 	
 Time to first mild, moderate or severe exacerbation Time to moderate or severe exacerbation Time to severe exacerbations Time to clinically important deterioration (CID) composite endpoint Time to clinically important deterioration composite endpoint excluding FEV₁ Rescue albuterol/salbutamol use, (percentage of rescue-free days and mean number of Inhalations/day) captured by the electronic diary (eDiary) over 24 weeks Inspiratory capacity (IC) Full Vital capacity (FVC) Change from baseline in trough FEV₁ Change from baseline in global impression of disease severity

Objectives	Endpoints
Safety	

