9.4.2. Other Analyses

The MMRM analysis will be repeated for the ITT ICS free population. Estimated differences between UMEC/VI or UMEC and Salmeterol will be presented together with 95% confidence intervals (CIs) for the difference and p-values.

Secondary and other efficacy endpoints and treatment comparisons will be adjusted for multiplicity as per Section [9.4.1](#).

Full details of the analyses to be performed on the other efficacy endpoints will be given in the RAP.

Safety Analyses

Adverse events (AEs) will be coded using the standard GSK dictionary, Medical

Dictionary for Regulatory Activities (MedDRA), and grouped by body system. The number and percentage of subjects experiencing at least one AE of any type, AEs within each body system and AEs within each preferred term will be presented for each treatment group. Separate summaries will be provided for all AEs, drug related AEs, fatal AEs, non-fatal SAEs, AESIs and AEs leading to withdrawal.

Deaths and SAEs will be documented in case narrative format.

Full details of the analyses to be performed on all safety endpoints will be given in the RAP.

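### The gate on the primary test controls multiplicity only for the Week 24 trough FEV1 comparisons; all other endpoints are tested at an unadjusted 5% although the protocol calls them adjusted

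*Protocol*

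**What the plan says.** Protocol section 9.4.1 gives the aim: "In order to account for multiplicity across treatment comparisons and endpoints, a step-down closed testing procedure will be applied". The operating rule is that inference on everything else is "dependent upon statistical significance having been achieved for the primary comparison". Once that test has p below 0.05, three groups of tests open at once: UMEC/VI versus UMEC on every other endpoint, and "UMEC/VI versus Salmeterol and UMEC versus Salmeterol on all endpoints including the primary endpoint". Each result is one "which will be declared statistically significant if the associated p-value is below 0.05". The section gives no order among these tests, no stopping rule after the first step and no division of alpha.

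Section 9.4.2 adds: "Secondary and other efficacy endpoints and treatment comparisons will be adjusted for multiplicity as per Section" 9.4.1. It supplies no further method.

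The scope is limited: "The step-down closed testing procedure only applies to the ROW". The G-BA analysis has no gate. Under section 9.4 the salmeterol comparisons "will be performed on the ITT population and ITT ICS free population".

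**The concern.** A closed or step-down procedure controls the family-wise error because each rejection depends on tests of intersection hypotheses, or on a fixed order that halts at the first failure. The rule in 9.4.1 has one such dependency, on the primary test. The later tests do not depend on one another.

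The affected results matter to this trial. Section 9.2 sizes it on TDI because comparing health-related quality of life is an important aim. The PRO endpoints are the whole secondary tier in section 3. Under 9.4.2 their p-values would be reported as multiplicity-adjusted when nothing beyond the gate has been applied.

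**Working it through.** **Inputs.** From section 9.2: two-sided 5%; 727 evaluable per arm; TDI SD 2.94 and difference 0.5; trough FEV1 SD 240 mL and difference 80 mL. From section 3: the secondary list. The correlation between endpoints is not in the protocol and is an assumption here, taken as 0.3 to 0.9.

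**1. The protocol's own figures reproduce.** n = 2 × (1.960 + 1.282)² × 2.94² / 0.5² = 726.6, so 727 per arm. 727 / 0.9 = 807.8, so 808 randomised.

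**2. How often the gate opens.** SE = 240 × √(2/727) = 12.59 mL. 80 / 12.59 = 6.355. Power = Φ(6.355 − 1.960) = 0.99999. If the drug works as planned, the gate filters out almost nothing.

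**3. What the gate does control.**
- If the primary null is true, any later false claim first needs the gate to open, which has probability 5%. Overall error is 5%.
- If the primary null is false, at most one of the two salmeterol nulls on Week 24 trough FEV1 can be true, because both together would make UMEC/VI equal to UMEC. One true null tested at 5% gives at most 5%.
- Simulating the gated rule on this endpoint (1,000,000 runs) gives 0.050 with all arms equal, 0.050 with UMEC equal to salmeterol, and 0.050 with UMEC/VI equal to salmeterol.

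**4. One other endpoint, three comparisons, gate open.** With three equal arms, at least one |Z| exceeds 1.96 when the range of three standard normals exceeds 1.96 × √2 = 2.772. That probability is 0.122, or about 12%.

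**5. The secondary list.** There are eight entries: mean and responder versions for TDI, E-RS, SGRQ-C and CAT. One of them reads "Assessment of respiratory daily symptoms over 24 weeks using Evaluating Respiratory Symptoms-COPD (E-RS) and its subscales". Counting three subscales and two E-RS responder cut-offs separately gives 8 + 3 + 1 = 12. Three comparisons make 24 or 36 tests.

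The table shows the chance of at least one |Z| above 1.96 (200,000 runs), with three arms that share arm means, equicorrelated endpoints, every PRO null true and the gate open:

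| Assumed correlation | 8 endpoints, 24 tests | 12 endpoints, 36 tests |
|---|---|---|
| 0.3 | 59.0% | 71.9% |
| 0.5 | 50.8% | 61.0% |
| 0.7 | 40.1% | 46.9% |
| 0.9 | 26.6% | 29.5% |

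The endpoints in the protocol's other tier and the ICS-free repeats are not counted. The ICS-free set is nested in ITT, so its tests are strongly correlated with the ITT tests; their addition is not quantified here.

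**The case against.** A reader might infer that the plan has no multiplicity control at all. Step 3 shows otherwise: the primary test, the case where the primary null is true, and all three Week 24 trough FEV1 comparisons are held at 5%. For the same reason the 12% figure does not apply to Week 24 trough FEV1, only to other endpoints.

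A reader might also take the table as the error rate to expect. It is a worst case. It supposes that the arms do not differ on any PRO while FEV1 differs enough to open the gate, whereas section 9.2 plans for a 0.5-unit TDI difference. The endpoints also overlap: a total with its own subscales, a mean with its own responder version, two cut-offs on one score. High correlation is therefore plausible, and the lower rows deserve weight. This stands, and it is why the range runs to 0.9. It does not restore control, because strong control has to hold whichever nulls are true, and even the lowest figure is more than five times 5%.

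Two further points are fair. The 0.05 threshold is stated openly, so a reader is misled about the label and not about the cut-off. The primary conclusion and the sample size are untouched. However, the RAP cannot be presumed to cure this. The protocol leaves analysis details to the RAP but fixes the rejection rule itself, so an added order or alpha split would depart from 9.4.1.

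**Conclusion.** The point holds for endpoints other than Week 24 trough FEV1. Sections 9.4.1 and 9.4.2 claim multiplicity control across endpoints and comparisons that the stated rule does not deliver once the gate is open, and at the planned effect the gate opens with more than 99.9% probability. The worst-case chance of at least one false claim is about 12% for the three comparisons on one such endpoint. Over the secondary PROs it is about 27% to 59% (24 tests) or 30% to 72% (36 tests). These ranges rest on all PRO nulls being true and on assumed equal correlations of 0.9 to 0.3. The control of the primary test and of the three Week 24 trough FEV1 comparisons stands. The G-BA analysis is outside the procedure and outside this point.

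**What to change.** For the ROW analysis, reword 9.4.1 and 9.4.2 so that multiplicity control is claimed only for the three Week 24 trough FEV1 comparisons in the ITT population, and label all other p-values nominal.

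If a controlled PRO claim is wanted, pre-specify a short sequence that stops at the first failure and keeps overall family-wise error at 5%. It would start with the primary test and include the two FEV1 comparisons with salmeterol and TDI at Week 24 for UMEC/VI versus UMEC. After the primary test the full 5% cannot go to TDI and to the salmeterol pair in parallel. The sponsor has to choose:
- **TDI directly after the primary test at 5%.** TDI keeps about 90% power with 727 per arm (0.99999 × 0.900). The FEV1 comparisons with salmeterol then wait behind a test with about a 10% chance of failing under the planning assumptions.
- **The FEV1 comparisons with salmeterol first, as already gated.** TDI is tested at 5% only if both are significant. The protocol gives no planned difference against salmeterol, so the resulting TDI power cannot be stated.
- **A split, for example 2.5% each.** TDI power falls to Φ(0.5/0.1542 − 2.241) = Φ(1.001), about 84%, where 0.1542 = 2.94 × √(2/727).

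The cost is protocol and RAP wording, with no extra patients. The downside is that fewer endpoints can be called statistically significant. SGRQ-C, CAT and E-RS would be nominal unless the sponsor adds them to the sequence.

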9.4.2. Other Analyses

The MMRM analysis will be repeated for the ITT ICS free population. Estimated differences between UMEC/VI or UMEC and Salmeterol will be presented together with 95% confidence intervals (CIs) for the difference and p-values.

Secondary and other efficacy endpoints and treatment comparisons will be adjusted for multiplicity as per Section [9.4.1](#).

Full details of the analyses to be performed on the other efficacy endpoints will be given in the RAP.

Safety Analyses

Adverse events (AEs) will be coded using the standard GSK dictionary, Medical

Dictionary for Regulatory Activities (MedDRA), and grouped by body system. The number and percentage of subjects experiencing at least one AE of any type, AEs within each body system and AEs within each preferred term will be presented for each treatment group. Separate summaries will be provided for all AEs, drug related AEs, fatal AEs, non-fatal SAEs, AESIs and AEs leading to withdrawal.

Deaths and SAEs will be documented in case narrative format.

Full details of the analyses to be performed on all safety endpoints will be given in the RAP.

10. STUDY GOVERNANCE CONSIDERATIONS

10.1. Posting of Information on Publicly Available Clinical Trial Registers

Study information from this protocol will be posted on publicly available clinical trial registers before enrollment of subjects begins.

10.2. Regulatory and Ethical Considerations, Including the Informed Consent Process

Prior to initiation of a site, GSK will obtain favourable opinion/approval from the appropriate regulatory agency to conduct the study in accordance with ICH Good Clinical Practice (GCP) and applicable country-specific regulatory requirements.

The study will be conducted in accordance with all applicable regulatory requirements, and with GSK policy.

Study site Investigators will be selected to participate in the 201749 study based upon their pulmonology expertise and knowledge of the protocol defined patient population and associated required study assessments.

The study will also be conducted in accordance with ICH Good Clinical Practice (GCP), all applicable subject privacy requirements, and the guiding principles of the current version of the Declaration of Helsinki. This includes, but is not limited to, the following:

- IRB/IEC review and favorable opinion/approval of the study protocol and amendments as applicable
- Obtaining signed informed consent
- Investigator reporting requirements (e.g. reporting of AEs/SAEs/protocol deviations to IRB/IEC)
- GSK will provide full details of the above procedures, either verbally, in writing, or both.
- Signed informed consent must be obtained for each subject prior to participation in the study
- The IEC/IRB, and where applicable the regulatory authority, approve the clinical protocol and all optional assessments, including genetic research.
- Optional assessments (including those in a separate protocol and/or under separate informed consent) and the clinical protocol should be concurrently submitted for approval unless regulation requires separate submission.
- Approval of the optional assessments may occur after approval is granted for the clinical protocol where required by regulatory authorities. In this situation, written approval of the clinical protocol should state that approval of optional assessments is being deferred and the study, with the exception of the optional assessments, can be initiated.

10.3. Quality Control (Study Monitoring)

- In accordance with applicable regulations including GCP, and GSK procedures, GSK monitors will contact the site prior to the start of the study to review with the site staff the protocol, study requirements, and their responsibilities to satisfy regulatory, ethical, and GSK requirements.
- When reviewing data collection procedures, the discussion will also include identification, agreement and documentation of data items for which the eCRF will serve as the source document.

GSK will monitor the study and site activity to verify that the:

- Data are authentic, accurate, and complete.
- Safety and rights of subjects are being protected.
- Study is conducted in accordance with the currently approved protocol and any other study agreements, GCP, and all applicable regulatory requirements.

The investigator and the head of the medical institution (where applicable) agrees to allow the monitor direct access to all relevant documents

10.4. Quality Assurance

- To ensure compliance with GCP and all applicable regulatory requirements, GSK may conduct a quality assurance assessment and/or audit of the site records, and the regulatory agencies may conduct a regulatory inspection at any time during or after completion of the study.
- In the event of an assessment, audit or inspection, the investigator (and institution) must agree to grant the advisor(s), auditor(s) and inspector(s) direct access to all relevant documents and to allocate their time and the time of their staff to discuss the conduct of the study, any findings/relevant issues and to implement any corrective and/or preventative actions to address any findings/issues identified.

10.5. Study and Site Closure

- Upon completion or premature discontinuation of the study, the GSK monitor will conduct site closure activities with the investigator or site staff, as appropriate, in accordance with applicable regulations including GCP, and GSK Standard Operating Procedures.
- GSK reserves the right to temporarily suspend or prematurely discontinue this study at any time for reasons including, but not limited to, safety or ethical issues or severe non-compliance. For multicenter studies, this can occur at one or more or at all sites.
- If GSK determines such action is needed, GSK will discuss the reasons for taking such action with the investigator or the head of the medical institution (where applicable). When feasible, GSK will provide advance notification to the investigator or the head of the medical institution, where applicable, of the impending action.
- If the study is suspended or prematurely discontinued for safety reasons, GSK will promptly inform all investigators, heads of the medical institutions (where applicable) and/or institution(s) conducting the study. GSK will also promptly inform the relevant regulatory authorities of the suspension or premature discontinuation of the study and the reason(s) for the action.
- If required by applicable regulations, the investigator or the head of the medical institution (where applicable) must inform the IRB/IEC promptly and provide the reason for the suspension or premature discontinuation.

10.6. Records Retention

- Following closure of the study, the investigator or the head of the medical institution (where applicable) must maintain all site study records (except for those required by local regulations to be maintained elsewhere), in a safe and secure location.
- The records must be maintained to allow easy and timely retrieval, when needed (e.g., for a GSK audit or regulatory inspection) and must be available for review in conjunction with assessment of the facility, supporting systems, and relevant site staff.

- Where permitted by local laws/regulations or institutional policy, some or all of these records can be maintained in a format other than hard copy (e.g., microfiche, scanned, electronic); however, caution needs to be exercised before such action is taken.
- The investigator must ensure that all reproductions are legible and are a true and accurate copy of the original and meet accessibility and retrieval standards, including re-generating a hard copy, if required. Furthermore, the investigator must ensure there is an acceptable back-up of these reproductions and that an acceptable quality control process exists for making these reproductions.
- GSK will inform the investigator of the time period for retaining these records to comply with all applicable regulatory requirements. The minimum retention time will meet the strictest standard applicable to that site for the study, as dictated by any institutional requirements or local laws or regulations, GSK standards/procedures, and/or institutional requirements.
- The investigator must notify GSK of any changes in the archival arrangements, including, but not limited to, archival at an off-site facility or transfer of ownership of the records in the event the investigator is no longer associated with the site.

10.7. Provision of Study Results to Investigators, Posting of Information on Publicly Available Clinical Trials Registers and Publication

Where required by applicable regulatory requirements, an investigator signatory will be identified for the approval of the clinical study report. The investigator will be provided reasonable access to statistical tables, figures, and relevant reports and will have the opportunity to review the complete study results at a GSK site or other mutually-agreeable location.

GSK will also provide the investigator with the full summary of the study results. The investigator is encouraged to share the summary results with the study subjects, as appropriate.

GSK will provide the investigator with the randomization codes for their site only after completion of the full statistical analysis.

The procedures and timing for public disclosure of the results summary and for development of a manuscript for publication will be in accordance with GSK Policy.

A manuscript will be progressed for publication in the scientific literature if the results provide important scientific or medical knowledge.

